**SAD Diagnostic Checklist**

**Hamilton Depression Rating Scale**

**Clinical Global Impression Scale of Improvement**

**Clinical Global Impression Scale of Severity**

**Patient Global Impression of Change**

**Penn Physician Withdrawal Checklist**

This statistical analysis plan (SAP) describes the planned analysis and reporting for VistaGen Therapeutics, Inc. protocol number PH94B-CL030 (A Phase 3 Open-label Safety Trial of PH94B Nasal Spray in the Acute Treatment of Anxiety in Adult Subjects with Social Anxiety Disorder (SAD)), dated 14-Mar-2022 Version 2.0. Reference materials for this statistical plan include the protocol and the accompanying sample data collection documents. Operational aspects related to collection and timing of planned clinical assessments are not repeated in this SAP unless relevant to the planned analysis.

The structure and content of this SAP provides sufficient detail to meet the requirements identified by the Food and Drug Administration (FDA), European Medicines Agency (EMA), and International Conference on Harmonization (ICH) of Technical Requirements for Registration of Pharmaceuticals for Human Use: Guidance on Statistical Principles in Clinical Trials (ICH, 1998). All work planned and reported for this SAP will follow internationally accepted guidelines, published by the American Statistical Association (ASA, 2018) and the Royal Statistical Society (RSS, 2014), for statistical practice.

The planned analyses identified in this SAP may be included in clinical study reports (CSRs), regulatory submissions, or future manuscripts. Also, post-hoc exploratory analyses not necessarily identified in this SAP may be performed to further examine study data. Any post-hoc or unplanned, exploratory analysis performed will be clearly identified as such in the final CSR.

The statistical plan described hereafter is an *a priori* plan. It will be approved before any analysis of data pertaining to VistaGen Therapeutic Inc.'s study PH94B-CL030.

2. Study Objectives and Endpoints

2.1. Study Objectives

2.1.1. Primary Objective

The primary objective is to evaluate the safety and tolerability of repeated dosing of PH94B over a period of up to 12 months as assessed by documenting adverse events (AEs) and standard clinical measurements (physical examination, vital signs, clinical chemistry, hematology, suicidality, level of depression, and 12-lead electrocardiogram [ECG]).

2.1.2. [REDACTED]

[REDACTED]

[REDACTED]

[REDACTED]

- [REDACTED]
- [REDACTED]
- [REDACTED]
- [REDACTED]
- [REDACTED]

2.2. Study Endpoints

2.2.1. Safety Endpoints

The safety endpoints of this study include the following:

- Incidence and severity of AEs, AEs leading to discontinuation, and SAEs
- Changes in vital signs results
- Changes in clinical laboratory evaluation (hematology, chemistry, and urinalysis) results
- Changes in 12-lead ECG results
- Changes in physical examination findings
- Changes in HAM-D17 scores
- Changes in C-SSRS scores
- PWC-20 scores after termination of PH94B

2.2.2. Exploratory Efficacy Endpoints

The exploratory efficacy endpoints of this study include the following:

- Change in total LSAS scores from baseline (Visit 2) to end of treatment (Visit 14)
- Change in proportion of subjects with CGI-S scores >4 from baseline (Visit 2) to end of treatment (Visit 14)
- Change in proportion of subjects with CGI-I scores of 1 (Very much improved) or 2 (Much improved) from first month (Visit 3) to end of treatment (Visit 14)
- Change in proportion of subjects with PGI-C scores of 1 (Very much improved) or 2 (Much improved) from first month (Visit 3) to end of treatment (Visit 14)
- [REDACTED]

3. Overall Study Design and Plan

Subject participation in the study will last up to approximately 12 to 13 months, depending on

AD-ST-33.06 Effective date: 12-Nov-2020

Version 0.3 | Date 17-Nov-2022 | AD-PR-109.02 Effective date: 17-Aug-2020

Page 11 of 99

the duration of the screening period and intervals between Visits. Upon signing the informed consent form (ICF), subjects will complete Visit 1 and enter a screening period lasting between 7 and 35 days. Subjects who meet all eligibility criteria will return to the clinic to complete Visit 2 (Baseline, Day 0) and undergo baseline measurements of clinical laboratory assessments (clinical chemistry, hematology, urinalysis, pregnancy test [if female and of childbearing potential], and urine drug screening), 12-lead ECG, vital signs, physical examination, Hamilton Rating Scale for Depression (HAM-D17), [REDACTED] Liebowitz Social Anxiety Scale (LSAS), Columbia-Suicide Severity Rating Scale (C-SSRS), and Clinical Global Impression Scale of Severity (CGI-S). At Visit 2 (Baseline), subjects will be trained on how to use and store the PH94B nasal spray delivery device, and how to use an electronic diary (eDiary) application; subjects will be instructed to record each incidence of PH94B use in the eDiary application. Adverse events (AEs) and concomitant medications will be reported and recorded. The subject will receive a [REDACTED] of PH94B [REDACTED] for use (up to 4 times per day) at the subject's discretion, as needed for social anxiety.

Subjects will be instructed to return to the clinic for Visit 3 after 30 days (± 3 days). At Visit 3, subjects will undergo clinical laboratory assessments (clinical chemistry, hematology, urinalysis, pregnancy test, and urine drug screening), vital signs, 12-lead ECG, physical examination, HAM-D17, [REDACTED] LSAS, C-SSRS, CGI-S, CGI-I, and self-evaluation by the patient-reported outcome measure, Patient Global Impression of Change (PGI-C). At Visit 3, PH94B use recorded in the eDiary application will be reviewed and AEs and concomitant medications will be reported and recorded. Subjects will receive a 1-month supply of PH94B (6 vials).

Subjects will return to the clinic at monthly intervals (± 7 days, Visits 4 to 13), and will repeat the same assessments as those performed at Visit 3. PH94B use recorded in the eDiary application will be reviewed, AEs and concomitant medications will be reported and recorded, and at each Visit subjects will receive a 1-month supply of PH94B (6 vials).

At Visit 14 (1 year ± 2 weeks), treatment will conclude, and subjects will undergo clinical laboratory assessments (clinical chemistry, hematology, urinalysis, pregnancy test, and urine drug screening), vital signs, 12-lead ECG, physical examination, HAM-D17, [REDACTED] LSAS, C-SSRS CGI-S, CGI-I, and PGI-C. Also, PH94B use recorded in the eDiary application will be reviewed, and AEs and concomitant medications will be recorded and reported. Subjects will also be informed of their follow-up Visit (Visit 15).

Subjects will return to the clinic for a follow-up Visit (Visit 15, 54 weeks ± 3 days), approximately 2 weeks after the last PH94B administration, to undergo C-SSRS and vital signs assessments, and record AEs.

Safety Considerations:

Safety and tolerability of PH94B (≤ 4 doses per day up to 12 months in up to 600 subjects) will be assessed and summarized through changes from baseline (Visit 2) to end of treatment (Visit 14) in AEs, laboratory values, 12-lead ECGs, physical examinations, and vital sign assessments following exposure to PH94B.

3.1. Overall Design

3.2. Sample Size and Power

Based on feedback from the FDA, the sample size for this study (up to 600 subjects) has been selected to attain a PH94B safety database per the ICH E1 Guideline.

3.3. Study Population

The study population consists of male or female subjects, 18 through 65 years of age, inclusive, with a current diagnosis of SAD and with no prior or current conditions that would increase risk of treatment or confound the results of the study.

3.4. Treatments Administered

The treatment to be administered is PH94B nasal spray, one spray to each nostril for a total dose of 3.2 μ g, up to four times a day.

3.5. Schedule of Events

Table 1 Schedule of Events

	Study Periods				
	Visit 1	Visit 2	Visit 3	Visits 4 to 13	Visit 14 / ET
Screening	Baseline	1st Month	Monthly	End of Treatment	Follow-up
Assessment/Evaluation	Day -35 to Day -7	Day 0	Day 30 ±3 days	±7 days	52 Weeks ±2 weeks
Informed Consent Form ^a	X	X			
Subject Demographics	X				
Medical and Psychiatric History	X				
Record Concomitant Medication Use	X	X	X	X	X
SAD Diagnostic Criteria Checklist	X				
Clinical Chemistry, Hematology, and Urinalysis	X	X	X	X	X
Urine Drug Screen	X	X	X	X	X
Pregnancy Test ^c	X	X	X	X	X
12-Lead Electrocardiogram ^d	X	X	X	X	X
Physical Examination ^e	X ^f	X	X	X	X

AD-ST-33-06 Effective date: 12-Nov-2020

Version 0.3 | Date 17-Nov-2022 | AD-PR-109.02 Effective date: 17-Aug-2020

	Screening	Baseline	1st Month	Monthly	Study Periods			
					Visit 1	Visit 2	Visit 3	Visits 4 to 13
Assessment/Evaluation	Day -35 to Day -7	Day 0	Day 30 ±3 days	±7 days	52 Weeks ±2 weeks	54 Weeks ±3 days	Follow-up	
Vital Signs	X	X	X	X	X	X		X
MINI 7.0.2	X							
LSAS	X	X	X	X	X	X		
HAM-D17	X	X	X	X	X	X		
C-SSRS	X	X	X	X	X	X		X
CGI-S	X	X	X	X	X	X		
CGI-I					X	X		X
PGI-C					X	X		
PWC-20						X		X
Training on Use of Spray Device					X			
Storage Instructions					X	X	X	
Training on eDiary App to Record PH94B Use					X			
Adverse Event Recording					X	X	X	X
Dispense PH94B to Subject					X	X	X	
eDiary Review					X	X	X	X

Abbreviations: C-SSRS = Columbia-Suicide Severity Rating Scale; CGI-I = Clinical Global Impression Scale of Improvement; CGI-S = Clinical Global Impression Scale of Severity; eDiary = electronic diary; ET = Early Termination
HAM-D17 = Hamilton Rating Scale for Depression (17 items); LSAS = Liebowitz Social Anxiety Scale; MINI = Mini-International Neuropsychiatric Interview; PGI-C = Patient Global Impression of Change; PWC-20 = Penn Physician Withdrawal Checklist; SAD = social anxiety disorder
Subjects entering the study having participated in a previous PH94B Phase 3 SAD study will sign an informed consent form for the present study at either Visit 1 or Visit 2, depending on when they enter the study (see [Error! Reference source not found.](#)).

a For subjects entering the study having participated in a previous PH94B Phase 3 SAD study, a review of inclusion and exclusion criteria will be conducted at either Visit 1 or Visit 2, depending on when they enter the study (see [Error! Reference source not found.](#)).

b Pregnancy tests will only be given to female subjects of childbearing potential and not post-menopausal females.

c 12-Lead electrocardiograms will be administered to subjects at the Screening and Baseline Visits and then every month during the study.

d Physical examination will include measurement of weight and an examination of the nasal passages. Height will be measured at Screening and at Visit 14.

e If total anosmia is suspected during review of the nasal passages at Visit 1, the Quick Olfactory Test (QOT) is to be administered.

f Note: Long-term C-SSRS will be administered at screening. All other C-SSRS will be "Since Last Visit".
Note: If central laboratory urine drug screen testing is positive for a subject, then the participation of the subject in the study may have to be discontinued. The Medical Monitor should be consulted on these cases. An unscheduled repeat urine drug screen may be obtained to investigate whether drug use is continuing.

4. Statistical Analysis and Reporting

4.1. Introduction

Data processing, tabulation of descriptive statistics, calculation of inferential statistics, and graphical representations will primarily use SAS (release 9.4 or higher). If the use of other software is warranted, the final statistical methodology report will detail what software was used for what purposes.

Continuous (quantitative) variable summaries will include the number of subjects (n) with non-missing values, mean, standard deviation (SD), minimum, and maximum.

Categorical (qualitative) variable summaries will include the frequency and percentage of subjects who are in the particular category or each possible value. In general, the denominator for the percentage calculation will be based upon the total number of subjects in the study population with non-missing values.

The minimum and maximum will be reported with the same degree of precision (ie, the same number of decimal places) as the observed data. Measures of location (mean and median) will be reported to 1 degree of precision more than the observed data and measures of spread (SD) will be reported to 2 degrees of precision more than the observed data.

Percentages <100% will be presented to 1 decimal place and percentages of 100% will be reported with no decimal place. Counts of zero will be presented without percentages.

Unless otherwise indicated, all statistical tests will be conducted at the 0.05 significance level using 2-tailed tests, and *P* values will be reported. Corresponding 95% confidence intervals (CIs) will be presented for statistical tests. The statistical tests will be descriptive with no adjustment for multiplicity.

This study is considered an exploratory study. Statistical tests will be interpreted in an exploratory sense only and will not be considered formal hypothesis tests.

4.2. Interim Analysis and Data Monitoring

No interim analyses are planned.

5. Analysis Populations

The following analysis populations are planned for this study:

- **Safety Population:** All subjects who are dispensed IP during Visit 2 (Baseline) will be included in the Safety population. All subjects will receive PH94B in an open label fashion. Adverse events (AEs) will be grouped by associated length of exposure and level of PH94B use.

Inclusion of subjects in the Safety Population will be determined prior to database lock.

6. General Issues for Statistical Analysis

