9.	An acute or chronic condition, including an infectious illness, uncontrolled seasonal allergies at the time of the study, or significant nasal congestion that potentially could affect drug delivery to the nasal chemosensory epithelium.
10.	Any current clinically significant and/or uncontrolled medical condition, based on medical history or as evidenced in screening assessments, such as COVID-19, HIV, cancer, stroke, congestive heart failure, uncontrolled diabetes mellitus, or any other medical condition or disease that, in the clinical judgment of the Investigator, could

	
place the subject at undue risk, interfere with study participation, or confound the results of the study.
 
 
11. Women who have a positive urine pregnancy test prior to IP administration. Women who are currently breastfeeding are not eligible.
 
12. History of cancer or malignant tumor not in remission for at least 2 years. Basal cell skin cancers are not exclusionary.
 
13. Subjects with clinically significant abnormalities in hematology, blood chemistry, urinalysis, 12-lead ECG, or physical examination identified at study entry or during the legacy study which, in the clinical judgment of the Investigator, could place the subject at undue risk, interfere with study participation, or confound the results of the study.
 

TEST PRODUCT	
Name: PH94B Nasal Spray
 
Dose, route, frequency: 3.2 µg administered as an intranasal (i.n.) solution (a 1.6-µg spray to each nostril per dose), up to 4 times a day.

CONTROL PRODUCT	
Not applicable

TREATMENT REGIMENS	
Treatment will be administered as needed at 3.2 µg per dose of PH94B (<math>\leq</math> 4 doses per day) from Visit 2 (Baseline) to Visit 14 (End of Treatment).
 
Treatment with PH94B should be self-administered as needed approximately 15 minutes prior to or during an anxiety-provoking social situation or event. Consecutive nasal administrations of IP should be [REDACTED], with no more than 4 administrations per day. Treatment does not need to be administered every day.

PLANNED STUDY SITES	
The study is designed as a multicenter study conducted in the USA with approximately 40 clinical study sites.

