## 13. STATISTICS

An interim safety analysis will be performed when approximately 100 subjects have completed 12 months of PH94B dosing up to 4 times per day and approximately 300 subjects have completed 6 months of PH94B dosing up to 4 times per day. All subjects who have received at least 1 dose of PH94B at this point will be included in this analysis. A final analysis will be performed after the last subject has completed or discontinued from the study.

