#### 13.1.1 Analysis Populations

A single analysis population is planned for this study:

- Safety population: All subjects who receive IP.

All analyses will be performed using the Safety population.

Primary and exploratory endpoints may be summarized by subgroups of interest including age, sex, concomitant medications, and SAD severity. Analysis of subgroups not pre-defined in the final SAP will be labeled as such in the clinical study report (CSR).

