Text formerly read:	If the partner of a male subject becomes pregnant during his IP treatment or within 14 days of his discontinuing the IP, the Investigator must report the pregnancy within 48 hours of learning of the pregnancy, to [REDACTED] Pharmacovigilance, as described above.
Now reads:	Male subjects with partners of childbearing potential should be advised to use contraception throughout their participation in the study. If the partner of a male subject becomes pregnant during his IP treatment or within 14 days of his discontinuing the IP, the Investigator must report the pregnancy within 48 hours of learning of the pregnancy, to [REDACTED] Pharmacovigilance, as described above.
Section 13.1.1.	Analysis Populations
Text formerly read:	Safety: All subjects who are dispensed IP will be included in the safety population.
Now reads:	Safety population: All subjects who receive IP.

---

Section 13.1.2.1.	Disposition and Withdrawals
Text formerly read:	The numbers of subjects randomized, completing, and withdrawing, along with reasons for withdrawal, will be tabulated. Details on the number of subjects participating in previous PH94B Phase 3 SAD studies will also be provided.
Now reads:	The numbers of subjects randomized, completing, and withdrawing, along with reasons for withdrawal, will be tabulated. Details on the number of subjects participating in the individual antecedent PH94B SAD studies will also be provided.
Section 13.1.2.2.	Protocol Deviations
Text formerly read:	Documentation of the deviations and corrective actions will be included in the data quality assessment during blinded review.
Now reads:	Documentation of the deviations and corrective actions will be included in the data quality assessment during review.
Section 13.1.2.3.	Demographics and Other Baseline Characteristics
Text formerly read:	For all participating subjects, baseline is defined as Visit 2. For subjects coming from previous PH94B studies (PALISADE-1 [PH94B-CL026] or PALISADE-2 [PH94B CL032]), Visit 2 assessments should be conducted as described in the schedule of events (Table 2-1). Demographics, medical and psychiatric history, MINI findings, SAD Diagnostic Criteria Checklists, and baseline characteristics such as gender, age, race, weight, height and baseline physical examination reports, and vital signs will be carried over.

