6.1.7. Derived Variables

6.1.7.1. General

- **Age** = Integer difference in years between the subject's date of informed consent and date of birth.
- **Change from Baseline to Visit X in Parameter Y** = Value at Visit X minus the value at Baseline (as defined in Table 2).
- **Percent Change from Baseline to Visit X in Parameter Y** = Change from Baseline to Visit X in Parameter Y divided by the value at Baseline (as defined in Table 2) multiplied by 100.
- **Shift from Baseline to Visit X in Parameter Y Categories** = Cross-tabulation of below the lower limit of the normal range, within the limits of the normal range, and above the upper limit of the normal range at Baseline (as defined in Table 2) versus at Visit X.
- **Height (cm) and Weight (kg)** = Height (cm) will be calculated as height (in) times 2.54. Weight (kg) will be calculated as weight (lb) times 0.4536.
- **Temperature (C°)** = Temperature (F°) -32 times 5 divided by 9.
- **Treatment duration** = Days in study (date of last Visit minus date of Visit 2 (Baseline)).
- **Days of exposure** = Date of Visit 14 (End of Treatment) minus date of Visit 2. [In the case Visit 14 is missing then the date of study completion will be used.]
- **PH94B use** = average weight of all 6 vials when dispensed – weight of all 6 vials when returned at subsequent visit, at each visit.

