8.1. Adverse Events

Treatment emergent AEs (TEAEs) are defined as:

- AEs with onset at the time of or following the start of treatment with IP through final Visit or follow-up phone call.
- AEs starting prior to the start of treatment with IP but increasing in severity or relationship at the time of, or following, the start of treatment with IP through Visit 14 (End of Treatment/Follow-Up).
- AEs that occur between Visit 14 and Visit 15.

Any medical condition that is present at the time that the subject is screened will be considered as baseline and not reported as an AE. However, if the study subject's condition deteriorates at any time during the study, it will be recorded as an AE.

The Investigator will record all reportable events with start dates occurring any time after informed consent is obtained until 7 days after the last day of study participation. Events will be followed for outcome information until resolution or stabilization. Missing and partially missing start dates will be imputed for the purpose of analysis as described in Section **Error! Reference source not found.**

All AEs, TEAEs, and serious AEs (SAEs) will be coded using the MedDRA dictionary, as discussed in Section **Error! Reference source not found.**

All AE data will be categorized as Severe > Moderate > Mild. Relationship of all AEs to IP will be categorized as related or not related. In the summaries showing severity and relationship to study drug, the event with the maximum severity or strongest relationship to study drug will be reported. If a particular event is missing the severity and/or relationship, then the strongest possible severity or relationship will be assumed for analysis (severity = severe, relationship = related).

An overall summary of TEAEs will be provided; this will present number and percent of subjects who reported at least 1 of the following: TEAE (including any TEAE, TEAEs by maximum severity, and related TEAEs), TEAE leading to discontinuation of the study drug, TEAE leading to discontinuation from the study, serious TEAEs, and SAEs leading to death. TEAEs will be summarized by two time periods (TEAEs which occur prior to Visit 14 and those that occur during or after Visit 14).

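### The SAP's Safety population is everyone dispensed spray at Visit 2, not everyone who took it; this departs from the protocol undeclared and can count never-dosed subjects as exposed

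*SAP*

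**What the plan says.** SAP Section 5 (Analysis Populations) sets a single population: "All subjects who are dispensed IP during Visit 2 (Baseline) will be included in the Safety population". The SAP overview ties the plan to the protocol "dated 14-Mar-2022 Version 2.0". In that version, Section 13.1.1 and the synopsis read "Safety population: All subjects who receive IP", and every analysis is run on that set.

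Two other places in Protocol Section 13 bear on what is meant. The opening of the section describes the interim safety analysis: "All subjects who have received at least 1 dose of PH94B at this point will be included in this analysis". Section 13.1.4 divides AE counts by the number of subjects exposed to the product in the period.

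Dosing is as needed and left to the subject; the synopsis adds "Treatment does not need to be administered every day".

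Two SAP rules then act on the population. The first part of the TEAE definition in SAP 8.1 is "AEs with onset at the time of or following the start of treatment with IP through final Visit or follow-up phone call". Days of exposure in SAP 6.1.7.1 are "Date of Visit 14 (End of Treatment) minus date of Visit 2", with the study completion date used if Visit 14 is missing. SAP Section 10 lists changes from the planned analysis; the Safety population is not among them.

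**The concern.** The trial asks whether repeated dosing is safe over up to 12 months, and its size of up to 600 is justified only as building a safety database. Every percentage therefore rests on who counts as treated. In a trial with a supervised first dose, dispensed and dosed would be nearly the same group. Here they need not be. A subject who never uses the spray contributes to the denominators and to exposure time without contributing information about the drug. If there are enough such subjects, the product looks somewhat better tolerated, and the exposed group larger, than the data support. The reader of the report could not tell, because no planned table counts them.

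**Working it through.** **1. Which text governs.** Both definitions are in force: the SAP's dispensed rule and the protocol's receive rule. The amendment summary in Protocol Appendix J shows that the superseded protocol text was "Safety: All subjects who are dispensed IP will be included in the safety population". That difference is not itself an error, but it shows that the sponsor moved away from dispensing as the criterion, and the SAP keeps the superseded criterion.

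**2. Can the two groups differ?** The protocol's Visit 2 procedures (10.2.2.1) cover assessments, training, eDiary instruction and dispensing, with no dose taken in clinic. Section 9.4.1 expects diary days with zero doses. So a dispensed subject can leave the trial, or stay in it, without dosing.

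**3. Numerator.** SAP 8.1 has three parts. The first two depend on a start of treatment, which a never-dosed subject lacks. The third counts AEs between Visit 14 and Visit 15 with no such condition.

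**4. Effect on incidence.** Let p be the true incidence among dosed subjects, f the never-dosed share of those dispensed, and b the proportion of never-dosed subjects who are counted with a TEAE. Then

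displayed incidence = (1 − f) × p + f × b.

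The documents give none of f, p or b. Assume p = 20% and 600 dispensed, and take b = 0 (the first two parts of the definition applied strictly):

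| f | never dosed | dosed | displayed |
|---|---|---|---|
| 0% | 0 | 600 | 20.0% |
| 1% | 6 | 594 | 0.20 × 594/600 = 19.8% |
| 5% | 30 | 570 | 0.20 × 570/600 = 19.0% |
| 10% | 60 | 540 | 0.20 × 540/600 = 18.0% |

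With b = 0 the relative understatement equals f. If b = p, the displayed figure is 20.0% whatever f is; if b exceeded p, the figure would be too high.

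**5. Effect on exposure.** If the never-dosed subjects all stayed 52 weeks (364 days), the time credited without drug would be 6 × 364/365.25 = 6.0, 30 × 364/365.25 = 29.9 or 60 × 364/365.25 = 59.8 person-years, out of 600 × 364/365.25 = 597.9. These are upper limits, since early leavers add fewer days.

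**6. Effect on ruling out rare events.** The one-sided 95% upper bound after zero events is 1 − 0.05^(1/n): 0.498% for n = 600, and 0.503%, 0.524% or 0.553% for 594, 570 or 540. This is a small change, and the SAP does not plan to report such a bound.

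The plan gives no precision calculation behind 600, so there is no figure of its own to reproduce.

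**The case against.** The protocol's word receive is ambiguous: it also describes subjects being handed a month's supply (7.1, 9.9.1). The stated reason for amending the populations is only simplification. The wording about at least one dose belongs to an interim analysis that the SAP has since dropped. All this is fair, and a reader should not infer that Protocol 13.1.1 itself says at least one dose; it does not. The dosed reading remains the better one: if receive meant dispensed, the amended definition would have changed nothing, and Section 13.1.4 speaks of subjects exposed.

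A reader might also infer that a never-dosed subject can never have a TEAE, so that the error can only make the product look safer. The documents do not support that. The third part of the TEAE definition can admit such a subject. If programmers take Visit 2 as the start of treatment, as the exposure formula does, all later background AEs of undosed subjects count too. The direction is likely on the SAP's main wording, but it is not proven.

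The SAP also has contrary text. Its baseline table (6.1.1) speaks of a first dose given at Visit 2, and 7.4 has site staff instructing self-administration from Visit 2. Neither matches a dosing step in the protocol's Visit 2 list, so this is a further inconsistency rather than an answer.

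SAP Section 5 promises AE grouping by level of use, and a table of use by visit is planned. This helps only partly: the AE tables listed in SAP 12.3 show no such split, and 8.1 divides TEAEs into two time periods only.

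Finally, the visit-date exposure formula credits a one-dose subject with the whole period as well. That is a separate weakness, which changing the population does not cure.

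**Conclusion.** The point holds as an undeclared contradiction between SAP and protocol on the trial's only analysis population, with a plausible but unquantified effect. AE percentages would tend to be too low by about the never-dosed fraction: 0.2, 1.0 or 2.0 percentage points on a true 20% at assumed fractions of 1%, 5% or 10%, and nothing if everyone dosed at least once. This rests on the assumed fraction and on never-dosed subjects rarely being counted with a TEAE. All safety analyses are descriptive, so no test or decision rule is affected. It is a should-fix: the size may be small, but the validity of the denominators should not depend on a number that the report will not show. It would go too far to claim a proven one-directional bias, or a full year of false exposure for each such subject.

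**What to change.** Change SAP Section 5 to subjects with evidence of at least one dose of PH94B, consistent with the protocol's intent, and specify that evidence:

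- **Main sources:** weight loss of returned vials beyond a pre-specified priming allowance, and any dose documented by the site. Vials are weighed before priming (Protocol 9.9.1) and the current text gives no priming loss, so the allowance must be set from device data. Use individual vial weights. One dose is 2 × 100 µL = 0.2 mL, and the SAP's averaging over six vials would reduce it to 0.2/6 = 0.033 mL.
- **Supporting source only:** eDiary doses, since SAP Section 10 calls those data unreliable.
- **No evidence either way** (for example, no diary and no returned vials): keep the subject in the population and report how many there are. Some undosed subjects may remain, but visibly.

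Report the number dispensed but never dosed in the disposition table, and give them no exposure days. State what date counts as start of treatment for TEAEs. Reconcile the first-dose-at-Visit-2 wording in the SAP's baseline table with the protocol's Visit 2 procedures. If the sponsor prefers to keep the dispensed set, declare it in SAP Section 10 and show the dosed set beside it.

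The cost is one definition, one derivation from data already collected, and one disposition row, all before the population is fixed at database lock. The reported N may fall slightly.
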